All original data and study documents will be maintained within the VAMC system. Only fully de-identified data will be transcribed from the existing electronic medical record system maintained by the VA or collected on case report forms. Only de-identified data will be entered into the web-based data management system developed and maintained by WFUHS. Access to the data management system will require password authentication and WFUHS will take full measures to minimize the risk of breaching the confidentiality of data including electronic firewalls, audit trails, and systems certification. WFUHS has coordinated a number of trials previously in which the VA participated including ACCORD, SPRINT, and ACCORDION and established systems to ensure that all data is managed to be compliant with VA policy and to meet the requirements for approval from the VA's Institutional Review Board. The WFUHS research team will complete research training and complete the verification and credentialing processes required of "Without Compensation" (WOC) employees through the VAMC system. Risks related to inadvertent release of confidential information will be minimized through adherence to best practices for data collection and management. All research staff will be trained in methods for assuring participant confidentiality and safety. The information we are collecting is not of a particularly sensitive nature and we will follow exacting procedures to maintain confidentiality of the participant level data. Identifying information will be kept separate from research data and will be linked only by a participant ID, generated so as to be independent of any identifying information. All original records will be maintained within the VAMC system. Only de-identified data will be released outside of the VAMC. No identifying information will be released in any published reports. Research study materials and documents will be maintained at the end of the study as required by VAMC directives under double lock.

VII. Human Subjects Protection

Approval to proceed with this project will be sought from the Institutional Review Boards (IRBs) of the Department of Veterans Affairs, Salisbury VAMC Medical Center and Wake Forest University Health Sciences and the Research and Development Committee of Salisbury VAMC. We will submit an informed consent document, including HIPAA authorization, to both IRBs as part of our application for approval. In dealing with human subjects, Both IRBs comply with all rules and regulations of the Department of Health and Human Services (DHHS) regarding the protection of human subjects (Title 45 CFR Part 46). The principal investigator and research team routinely complete formal education on the protection of human research participants and all new staff, including those participants in research-activities at the Kernersville Health Care Center, will be required to do so as well. The principal investigators and research team will complete and maintain all required VAMC research training and

NIH Information Security and Privacy Awareness Training. Investigators will participate in additional formal and informal training in research ethics and scientific integrity throughout the study provided from time to time by ethics educators affiliated with Wake Forest School of Medicine. A Manual of Procedures (MOP) will be developed for all aspects of the study, and the procedures will be strictly followed. All study personnel will receive formalized training that will cover all recruitment, informed consent, measurements, specimen handling, participant follow-up, adverse events, side effects, and reporting issues. Adherence to the procedures in the MOP will be assured by periodic assessment and retraining.

a. Subject Recruitment Methods

We plan to identify patients seen at the Kernersville Health Care Center who are at high risk for developing T2DM by engaging primary care providers in identifying potential participants and referring them to the program for participation. In this pilot study, we plan to identify opportunities to integrate the recruitment process into the existing healthcare delivery system by educating providers at all levels about the study, providing materials that they can share with patients at risk for developing diabetes, and developing support from clinic leadership to support our recruitment efforts. We hope to use the strategies identified in this pilot study to inform our recruitment efforts in a larger trial testing implementation in the VA system.

In order to reduce the need to collect additional information, screening and eligibility data will be collected from the existing medical record.

b. Informed Consent

Any patients interested and eligible for the study will be referred by clinic providers or staff to the nurse or diabetes educator affiliated with the project for eligibility verification and administration of informed consent. At that time, the nurse or diabetes educator will inform potential participants of the study design and interventions, the risks and benefits of participation, their rights and responsibilities as research participants, and alternatives to participation. Participants will also be informed that participation is voluntary and that they can withdraw from the study if their initial or on-going experience makes it oppressive, burdensome, or otherwise uncomfortable. All participants will be required to sign informed consent and HIPAA documents prior to randomization. The informed consent and HIPAA documents will include a required text as defined by the Salisbury VAMC IRB.

c. Confidentiality and Privacy

Confidentiality will be protected by collecting only information needed to assess study outcomes, minimizing to the fullest extent possible the collection of any information that could directly identify subjects, and maintaining all study information in a secure manner. As stated previously, original data and study documents will be maintained within the VAMC system. Only fully de-identified data will be transcribed from the existing electronic medical record system maintained by the VA or collected on case report forms. Only de-identified data will be entered into the web-based data management system developed and maintained by WFUHS. To help ensure subject privacy and confidentiality, only a unique

study identifier will appear on the data collection form. Any collected patient identifying information corresponding to the unique study identifier will be maintained on a linkage file, stored separately from the data. The linkage file will be kept secure, with access limited to designated study personnel. Subject identifying information will be destroyed three years after closure of the study, consistent with data validation and study design, producing an anonymous analytical data set. Data access will be limited to study staff. Data and records will be kept locked and secured, with any computer data password protected. No reference to any individual participant will appear in reports, presentations, or publications that may arise from the study.

d. Data and Safety Monitoring

Personally identifiable information (name, address, date of birth, etc.) will be stored in an electronic database, on a local hard drive physically separate from the database storing research data, on a password protected computer within the VAMC system following all stipulations as required by VAMC Directives. This information will be kept completely separate from de-identified study data entered into the web-based data management system. Permission to view subject information will be available only to the Principal Investigator at the Salisbury VAMC or designee, as regulated by password authentication. Data obtained from this study are strictly for research purposes and will be stored in a de-identified manner in a web-based data management system maintained by WFUHS, as described above. During the sessions, each participant will report any discomfort and difficulties with the study protocol to the research staff as they occur. The PI on an individual basis will carefully and immediately review these reports. Furthermore, a monthly meeting of the research team will review the safety data and modify or stop the study protocol if necessary. No adverse effects are expected. In the event of an adverse event, a VAMC Adverse Event Report form will be completed and returned to the IRBs at both facilities within 5 working days.

As this pilot study is considered only a minor increase over minimal risk, we will utilize a Safety Officer, [name], MPH, to monitor participant safety and any reported events. Working with [name], we will also develop interim boundaries for monitoring the effect of the intervention on the primary outcome over time. All data reported to [name] will be fully de-identified.

Table 3. Blood Pressure Alert Values

Measure	Alert Value	Notify Participant	Notify PCP/Safety Officer
Blood Pressure (Avg.)	Level 1 SBP ≥ 180 mm/Hg OR DBP ≥ 110 mm/Hg	In clinic. Advise to follow-up with PCP within 1 week.	Within 1 week. IF symptomatic (e.g. chest pain, headache, short of breath), notify safety officer and/or PCP immediately.
	Level 2 SBP ≥ 160 mm/Hg OR DBP ≥ 100 mm/Hg (and not Level 1 BP)	In clinic. Advise to follow-up with PCP within 1 month.	Within 1 week. IF symptomatic (e.g. chest pain, headache, short of breath), notify safety officer and/or PCP immediately.
	Level 3 SBP ≥ 140 mm/Hg OR DBP ≥ 90 mm/Hg (and not Levels 1 or 2)	In clinic. Advise to follow-up with PCP within 2 months.	Per routine reporting. IF symptomatic (e.g. chest pain, headache, short of breath), notify safety officer and/or PCP immediately.
	SBP ≤ 90 mm/Hg OR DBP ≤ 50 mm/Hg	In clinic. Advise to follow-up with PCP within 1 week.	Within 1 week. IF symptomatic (lightheaded, feels faint), notify safety officer and/or PCP immediately.

e. Medical Alerts

All laboratory values used as outcome measures in this study are being collected from the existing medical record of each participant- no additional laboratory tests are being performed which could result in the need for alert values. Abnormal blood pressure measurements during the baseline and follow-up visits will be provided to the participant and his or her primary care provider (PCP) as described in Table 3 below. [name], the Safety Officer, and [name], the Principal Investigator will review medical eligibility criteria as needed, as well as measures collected during baseline and follow-up visits. These individuals also will serve as the primary contacts for staff, participants, and their PCPs regarding medical issues. [name] will review summaries of blood pressure alert values on a periodic basis along with any safety events.

f. Reporting of Unanticipated Problems, Adverse Events or Deviations

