Evidence of Pre-Diabetes: As we plan to identify participants in a clinical setting, all participants will be required to qualify based on evidence of prediabetes from fasting plasma glucose, oral glucose tolerance test, or HbA1c taken in the three months. The appropriate ranges for each test are 1) HbA1c: 5.7 to 6.4%; 2) Fasting Plasma Glucose: 95-125 mg/dL; 3) Oral Glucose Tolerance Test: 140-200 mg/dL. Blood measures will be collected from the medical record.

Willingness to Accept Randomization: Prospective participants must be willing to accept randomization to either the intensive lifestyle intervention or the comparison intervention condition.

ii. Exclusion Criteria

Weight Loss: Currently involved in a supervised program for weight loss.

Diabetes: Clinical history of diabetes.

Recent History of Cardiovascular Disease: Clinical history of cardiovascular disease (CVD) occurring within the past 6 months, including myocardial infarction, angina, coronary revascularization, stroke, TIA, carotid revascularization, peripheral arterial disease, and congestive heart failure. All persons with recent CVD should be participating in cardiac rehabilitation (with appropriate supervision as indicated) to reduce their risk of recurrence; hence, randomization might raise ethical concerns.

Hypertension: Uncontrolled high blood pressure: $\text{BP} > 160/100 \text{ mmHg}$. Potential participants can be rescreened after controlled.

Pregnancy, planning pregnancy and breast feeding (self-report) during screening: Pregnancy, breast feeding, or planning pregnancy within the next year.

Other Chronic Conditions: Other chronic disease likely to limit lifespan to less than 2-3 years, including any cancer requiring treatment in past 5 years except non-melanoma skin cancer.

Medication: Chronic use of medicine known to significantly affect glucose metabolism (e.g., corticosteroids, protease inhibitors).

Other: Conditions/criteria likely to interfere with participation and acceptance of randomized assignment, including the following: inability/unwillingness to give informed consent, another household member already randomized to HELP PD Vets, major psychiatric or cognitive problems (schizophrenia, dementia, self-reported active illegal substance or alcohol abuse), participation in another research study that would interfere with HELP PD Vets.

d. Sample Size

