We will collect information regarding demographics, anthropometry (height, weight, and waist circumference), blood pressure, medical history, health behaviors and behavioral constructs and health-

related quality of life (HRQL). The frequency with which study measures will be collected is outlined in Table 2.

a. Demographics

Age (date of birth), gender, race and ethnicity (US Census Definition), and names and contact information will be collected.

b. Blood pressure and anthropometry

Blood pressure, height, and weight will be collected from the most recent clinical encounter in the participant's existing medical record within the VA. This data will be used to both confirm eligibility for the trial and to serve as baseline and follow-up data.

c. Medical history and current medications

During screening, medical history of T2DM, cardiovascular disease and other medical conditions described above will be obtained to implement the inclusion and exclusion criteria. Medications that have the potential to impact blood glucose, lipid levels and body weight will be collected. This information will be obtained from the electronic medical record. Throughout the study, adverse and serious adverse events will be tracked.

d. Laboratory measures

Based on the current standard of care provided to patients in VA CBOCs, participants who are diagnosed with prediabetes are seen every 6 months and fasting blood is collected at those visits. Staff at the Kernersville Health Care Center will be able to obtain laboratory values to verify eligibility for participation and to serve as baseline and follow-up data from the participant's existing electronic medical record including hemoglobin A1c, fasting glucose, lipids and lipoproteins.

e. Physical activity

We will use the International Physical Activity Questionnaire (IPAQ), a reliable and valid instrument for assessing physical activity⁴². The IPAQ short form is a 7-item index that asks respondents the number of days per week and the amount of time per day spent in vigorous- and moderate-intensity

Table 2. Pilot Study Data Collection: Measures and Frequency

	Screening	Baseline	6-months
Informed Consent and HIPAA Authorization	X		
Demographics	X		
*Medical History	X		X
*Blood Pressure	X		X
*Height, Weight	X		X
*Current Medication Use		X	X
*HbA1c, *Fasting Glucose, *Lipids		X	X
3-day food records		X	X
International Physical Activity Questionnaire (IPAQ)		X	X
Veterans RAND36 (VR-36)		X	X

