**Measure obtained from medical record*

activities and walking, during the seven days prior to the interview. Different levels of physical activity are assigned metabolic equivalent (MET) scores based on the Compendium of Physical Activity and, using MET-minutes, can be converted to both continuous and categorical values. Using the IPAQ in HELP PD Vets will enable us to compare changes in physical activity with other trials, including the original HELP PD study.

f. Health-related quality of life (HRQL)

The Veterans RAND 36 (VR-36) Item Health Survey will be collected^{43, 44}. The VR-36 differs from the RAND 36 in the use of 5-point response choices for two of the eight scales, role limitations due to physical and emotional problems. The eight domains of the VR-36 include physical functioning, role limitations due to physical problems, bodily pain, general health perceptions, vitality, social functioning, role limitations due to emotional problems and mental health. The eight scales are summarized into physical and mental summary scores. The summaries are standardized using a t-score transformation and are normed to a U.S. population at a score of 50 and a standard deviation of 10⁴⁵.

g. Diet records

During screening, potential participants will be instructed to write down all foods and beverages consumed during the day prior to their baseline visit. A reminder call will be made to candidates two days prior to their visit to remind them of the visit and to remind them to start documenting their intake the next day. These diet records will serve two purposes: 1) to provide the study dietitian with baseline diet information to allow for tailored nutrition counseling, and 2) to assess changes in dietary intake pre- and post- intervention and compare dietary intake between intervention and EUC group participants. These food records will be analyzed using the Nutrition Data System for Research (Minneapolis, MN).

h. Cost estimation

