We will conduct a preliminary cost estimation of HELP PD Vets. Direct medical cost is a close proxy for what the intervention delivery would cost a large healthcare provider, such as the Veteran's Administration, a hospital, or insurance company. These direct costs will include the implementation of the lifestyle intervention and side effects of the intervention. We will estimate cost by relying on records of personnel and material costs and records of the number of participants attending intervention sessions; this information will be jointly collected by Wake Forest and staff from the Kernersville Health Care Center. Since this is a feasibility pilot study, we will not attempt the expensive and labor-intensive process of collecting and analyzing all data on cost, outcomes and efficacy associated with this trial from all possible standpoints, as would be required in a full-scale cost-effectiveness analysis. We will propose such an analysis in the full-scale R18 study.

i. Intervention evaluation

Participants randomized to the lifestyle intervention will be asked to complete a brief, anonymous evaluation at the conclusion of the 6-month close-out visit. This evaluation will capture qualitative data on the conduct of the intervention, participants' interaction with members of the study team, and each

participants' experience in the weight-loss components of the study. The data collected on this evaluation will not be linked to study-related process or outcome data as no ID number, acrostic, or other identifier will be collected. Prior to completing the survey, participants will be provided with a cover letter explaining the purpose of the evaluation and explaining that completion is voluntary. Participants will be provided the opportunity to ask questions about the evaluation and can refuse to complete it at their discretion. The data collected from this evaluation will inform intervention conduct and design in a larger trial.

VI. Analytical Plan

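### The labs labelled 6-month are not tied to randomization, and the source of follow-up weight and blood pressure is described in two ways; the result may be modest attenuation

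*Combined protocol and SAP*

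**What the plan says.** **Labs.** Section V.d relies on the standard of care, under which "participants who are diagnosed with prediabetes are seen every 6 months and fasting blood is collected at those visits". Eligibility, baseline and follow-up values are all read from the electronic record. Section VII.e confirms that "All laboratory values used as outcome measures in this study are being collected from the existing medical record" and that "no additional laboratory tests are being performed which could result in the need for alert values". The inclusion criteria (Section III.c.i) accept evidence of prediabetes from "fasting plasma glucose, oral glucose tolerance test, or HbA1c taken in the three months", without saying which date the three months run back from.

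**Weight and blood pressure.** Section V.b states "Blood pressure, height, and weight will be collected from the most recent clinical encounter" in the VA record, and then: "This data will be used to both confirm eligibility for the trial and to serve as baseline and follow-up data". The footnote to Table 2 ("Measure obtained from medical record") marks the same rows, including their entries in the 6-month column. Elsewhere the plan describes visits. Section VI has VA medical staff collecting data at baseline and at 6 months, Section VII.e speaks of blood pressure measured at the baseline and follow-up visits, and Section V.i places an "anonymous evaluation at the conclusion of the 6-month close-out visit".

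**Use.** Aim 2D seeks means and SDs of anthropometric and blood measures. Section III.d uses the variability estimates to size a later trial on blood glucose, and the effect estimates to judge whether the desired effects are feasible.

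**The concern.** Nothing links the routine draw to the randomization date, gives a window for the 6-month column, or says which draw counts. The lab reported as a 6-month value may therefore reflect less than the full six-month programme.

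For weight and blood pressure the protocol gives a rule, and the rule has no date limit. Followed literally, it can return an off-time value, or one that predates randomization, as the follow-up outcome. The visit-based account would avoid this, but the two accounts are not reconciled, and no section says that weight is measured at the close-out visit.

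At stake is what the effect estimates for labs, and possibly for weight and blood pressure, refer to. Recruitment, retention, adherence, cost, the IPAQ, the VR-36 and the food records are untouched.

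**Working it through.** **The plan's own precision.** Inputs from Section III.d: 50 participants, 16% dropout, 95% confidence. Completers = 50 × 0.84 = 42, or 21 per arm. Half-width = 1.96 × √(2/21) = 0.605 SD, which reproduces the stated ±0.6 SD.

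**When the lab falls.** Let a be the age of the qualifying lab at screening (0 to 3 months), g the gap from screening to randomization, and 6 months the draw interval. The next punctual draw is at month 6 − a − g.
- g = 0: months 3 to 6.
- g = 1 (assumed): months 2 to 5.
- g = 0, draws one month late: months 4 to 7.

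This requires that the qualifying test was itself a routine draw and that the next draw is the one used.

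**Share of the month-6 effect seen.** Assume a uniform on 0 to 3 and g = 0. The mean draw time is then month 4.5, with SD 3/√12 = 0.87, and one third of participants have a lab within a month of month 6. The documents do not say how fast the effect accrues, so four shapes are shown, each linear up to its plateau:

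| Accrual | Share seen | Of 5.1 mg/dL |
|---|---|---|
| Linear to month 6 | 4.5/6 = 0.75 | 3.8 |
| Plateau at month 5 | (2/3)(4/5) + 1/3 = 0.87 | 4.4 |
| Plateau at month 4 | (1/3)(3.5/4) + 2/3 = 0.96 | 4.9 |
| Plateau at month 3 | 1.00 | 5.1 |

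The 5.1 mg/dL is the approximate 6-month glucose contrast for HELP PD in the background section: a fall of almost 4 in one arm and a rise of 1.1 in the other. The shortfall is 0 to 1.3 mg/dL. The table is sensitive to g: with g = 1 and linear accrual the share would be 3.5/6 = 0.58. If most labs are drawn close to entry, the share approaches 1.

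**Against the pilot's resolution.** The documents give no glucose SD. If it is 6 to 12 mg/dL (assumption), the half-width is 0.605 × 6 = 3.6 to 0.605 × 12 = 7.3 mg/dL. The largest tabulated shortfall is 1.3/12 to 1.3/6, or about 0.1 to 0.2 SD.

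**Cost of treating absent labs as missing.** If 10% of the 42 completers have no new lab, 38 remain: 1.96 × √(4/38) = 0.64 SD.

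**Cost of modelling time.** Estimating the month-6 effect with a treatment-by-time term multiplies the half-width by √(1 + (6 − 4.5)²/0.75) = 2, giving about 1.2 SD.

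**The case against.** The strongest reply is that months 3 to 6 is a derivation and not a figure in the plan. It rests on a clause with no reference date. Recruitment runs through providers referring patients seen at the clinic, so labs could cluster near entry and follow-up draws near month 6. That stands, and the range must be stated conditionally.

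It is also fair that the weight and blood pressure problem may be one of wording. A close-out visit run by VA staff and entered in the VA chart would naturally be the most recent encounter, and then nothing is lost. The Manual of Procedures may add rules. The calendar, tracking and validation functions in Section VI make an unnoticed stale value less likely. None of these sets a lab date or names the source of the follow-up weight.

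Stronger readings are tempting, and the documents do not support them:
- **Planned reuse of baseline values.** A reader might infer this from V.b. Table 2 and Section VI treat baseline and 6 months as separate measurement times, so reuse is unprevented but not intended, and its frequency is unknown.
- **A spurious difference between arms.** The age of the qualifying lab is fixed before allocation, so randomization balances draw timing in expectation.
- **A wrongly sized next trial.** Section III.d sizes that trial from variability, and no effect of lab timing on the SD has been shown.

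**Conclusion.** The point holds as a cheap improvement. Lab timing relative to randomization is unspecified, and the plan gives two unreconciled accounts of where follow-up weight and blood pressure come from. The possible consequence is attenuation of the month-6 effect. For labs it is 0 to 25%, assuming uniform lab age over three months, no gap before randomization, a punctual next draw and the accrual shapes above. A gap moves the draw earlier and late visits move it later. For weight and blood pressure there is no loss if the close-out visit is the charted encounter. The timing bias is small beside a half-width of ±0.6 SD in a pilot not powered for any outcome, but it would not shrink with a larger sample, and without recorded dates nobody could later say what the 6-month label meant.

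**What to change.** 1. Measure weight at the baseline and 6-month visits already planned in Section VI, for all randomized participants, and use it as the outcome value. Reconcile V.b and Table 2 with Sections VI and VII.e on the source of blood pressure.
2. Store the timing of every record-derived value as days from randomization, which suits the de-identification rules. Require follow-up values to post-date randomization, and use the post-randomization lab closest to month 6. Treat a participant with none as missing under the planned multiple imputation.
3. Where the clinic can, schedule the routine draw near the 6-month visit. No study draw is added.
4. Report the distribution of lab times. Any model with time since randomization should be descriptive only, given its loss of precision.

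The cost is one weighing per planned visit, one timing field per charted value, some scheduling effort and slightly fewer non-missing values (0.64 instead of 0.60 SD in the 10% example).
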